# **1.0 STUDY SUMMARY**

# **1.1 AIM AND HYPOTHESIS**

The objective of this project is to compare the efficacy of hyoscyamine to tamsulosin monotherapy in treating lower urinary tract symptoms in patients with indwelling double-J ureteral stents.

Ureteral stents are routinely used in a variety of urologic conditions. Unfortunately, indwelling ureteral stents commonly cause significant pain and discomfort due to irritation to the urinary system. Many studies have looked at methods to reduce these uncomfortable symptoms ranging from altering stent designs to pharmacologic therapies attempting to alleviate stent-discomfort. However, stent-related discomfort continues to be an issue and is often the cause of their removal earlier than planned. While the efficacy of certain alpha blockers and anticholinergics in treating stent-related symptoms have been studied, the data for the use of hyoscyamine in this setting is lacking. A literature search yielded no studies evaluating the use of hyoscyamine in this setting to date. We hypothesize that hyoscyamine (brand name Levsin) is equivalent to tamsulosin in treating lower urinary tract symptoms in patients with indwelling double-J ureteral stents due to its anticholinergic properties. Furthermore, we hypothesize that patients in the hyoscyamine arm will not require additional pain medications (e.g. Pyridium, narcotics) to help control stent-related discomfort compared to the tamsulosin arm.

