# **3.0 STUDY OBJECTIVES**

# **3.1 PRIMARY OBJECTIVE**

To evaluate the efficacy of hyoscyamine compared to tamsulosin in improving the lower urinary tract symptoms of patients with indwelling double-J ureteral stents as assessed by the validated Ureteral Stent Symptom Questionnaire (USSQ).

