# **5.3 STUDY PROCEDURES**

To assess ureteral stent symptoms, we will be conducting the Ureteric Stent Symptoms Questionnaire (USSQ). The USSQ was created by Joshi et al as an instrument to measure stentrelated morbidity. The USSQ has been validated as a reliable instrument to measure the impact of ureteral stents. This validated questionnaire has been used in many previous studies regarding stent pain. In our study, the USSQ will be conducted prior to stent placement, on POD1, POD7 (or just prior to the time of stent removal if the removal occurs prior to day 7), and POD30. Basic demographic information, stent duration, stent size, stone location/size and obstructing vs. non-obstructing (if applicable), post stent insertion complications, drug diary information and questionnaire responses will be entered into a REDCap database for storage and analysis. The stent diameter will be 6Fr for all patients in the study. The appropriate stent length will be assigned to the patient based on cross sectional imaging. If cross sectional imaging is not available then stent length with be measured using a open-ended catheter to measure ureteral length. A small portion of these patients will be seen in the emergency department or while they are having an acute pain episode, so we expect that some of the pre-stenting questionnaires may not provide an accurate baseline for symptoms in these patients, hence the POD30 questionnaire will be obtained.

After informed consent is obtained, the patient will be prospectively randomized to either treatment arm in an open-label fashion using REDCap's randomization function to determine which therapy they will receive after stent placement. In the event that a patient does not find relief with their particular treatment arm, they will be permitted to receive additional narcotics or Pyridium. Should the patient continue to have unrelieved symptoms, treatment crossover is allowed since the study is designed in an intent-to-treat fashion.

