# 5.4 STUDY DESIGN AND SAMPLE SIZE

Total sample size: 100

The study will be conducted as a randomized comparative effectiveness trial with two arms. Subjects will be randomized to one of two treatments WITH either hyoscyamine or tamsulosin. Our hypothesis is that the hyoscyamine is at least as effective as tamsulosin in treating lower urinary tract symptoms. Symptoms will be quantified using the Urinary Symptom Index (USI) of the validated Ureteral Stent Symptom Questionnaire (USSQ). To address the hypothesis, the study will be conducted as a non-inferiority trial, following the hypothesis that hyoscyamine is not inferior to tamsulosin by more than a 15% margin in terms of the USI. The sample size was estimated using the PowerTOST package for the R statistical environment, based on a nominal power of 80% and an alpha-level of .025 for the one-sided t-test. Our null hypothesis is therefore that the mean USI for those treated with tamsulosin is more than 15% greater than those treated with hyoscyamine, so that by rejecting it, we may conclude hyoscyamine is not-inferior to tamsulosin by more than a 15% margin of USI for treating lower urinary tract symptoms. Furthermore, we assume that the coefficient of variation (CV) for the mean Urinary Index Score

will be similar to that in Park, et al.20 The CV in that study for the Urinary Symptom Index at week 2 after stent placement for the tamsulosin group was approximately .25. This is slightly higher, but similar to the CV of .22 for the USI in Maldonado-Avila, et al. which collected data at week 1, and therefore should be slightly conservative.21 Using these assumptions, we estimated that the sample size for each arm would need to be approximately 47, in order to have the desired power.

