# **5.5 DATA ANALYSIS**

The main hypothesis of the non-inferiority of hyoscyamine to tamsulosin for treating lower urinary tract symptoms will be tested using a t-test for non-inferiority of the change in USI between POD1 and POD7 (or day of stent removal if removed before day 7) in each treatment arm. This should be slightly more powerful than the t-test at POD7 alone that we used to estimate the sample size, but there are not enough data available for the distribution at POD1 in order to make a good estimate of the change. The non-inferiority margin will be 15% of the change in USI. The primary analysis will be conducted as intention-to-treat (ITT). That is, subjects will be analyzed as belonging to the arm they were randomized to, irrespective of later crossover or other modifications. This approach is in line with the current statement on Consolidated Standards of Reporting Trials (CONSORT). Descriptive statistics will be used to describe the results from all USSQ domains at each timepoint (i.e. mean and standard deviation, along with confidence intervals for urinary symptom index, pain symptom index, etc.). We will also conduct non-inferiority tests of change in score for ITT with hyoscyamine versus tamsulosin for the other domains spanned by the USSQ, including pain symptom index, general health index, work performance index, and sexual matters between POD1 and POD7, although we may not be wellpowered to detect non-inferiority for these additional domains.

The secondary goal of determining if there are differences in the amount of additional medications need to treat stent-related discomfort between treatment arms will be examined primarily through descriptive statistics. The drug diaries of all subjects will be used to tabulate the kinds and amounts of additional medications used. For each subject, the number of days that additional medications were used will be counted. The proportion of days that additional medications were used will be calculated for each group and 95% confidence intervals will be calculated.

Finally, we will also calculate the informed consent rate, and the discontinuation rate for those patients needing to be removed from the study in each arm.

In all cases, a p-value  $\leq$  .05 will be taken as a statistically significant result.

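### Crossover is allowed and non-inferiority is tested by ITT only: this supports a claim about the starting treatment, but the aim, null and conclusion are worded as efficacy of the drug

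*Combined protocol and SAP*

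**What the plan says.** **The question asked.** Section 1.1 sets out to "compare the efficacy of hyoscyamine to tamsulosin monotherapy in treating lower urinary tract symptoms", and the primary objective in section 3.1 reads "To evaluate the efficacy of hyoscyamine compared to tamsulosin in improving the lower urinary tract symptoms". Section 5.4 frames the null around the people who received each drug: "the mean USI for those treated with tamsulosin is more than 15% greater than those treated with hyoscyamine" (cited here only for which groups it compares). On rejecting it, the plan intends that "we may conclude hyoscyamine is not-inferior to tamsulosin by more than a 15% margin of USI for treating lower urinary tract symptoms".

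**What patients may do.** Section 5.3 permits narcotics or Pyridium for inadequate relief, and then: "Should the patient continue to have unrelieved symptoms, treatment crossover is allowed since the study is designed in an intent-to-treat fashion". No crossover rate is assumed anywhere.

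**What is analysed.** Section 5.5 tests the change in the Urinary Symptom Index (USI) from POD1 to POD7, or to stent removal if earlier. Under its ITT rule, "subjects will be analyzed as belonging to the arm they were randomized to, irrespective of later crossover or other modifications". The tests on the other questionnaire domains are also ITT. No analysis that addresses crossover is named.

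**What is measured.** Section 5.3 states that "the USSQ will be conducted prior to stent placement, on POD1, POD7", followed by POD30. The section 5.6 schedule has no questionnaire between POD1 and POD7. A diary is kept daily until the stent is removed.

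**Pointing the other way.** Section 5.4 calls the study a "randomized comparative effectiveness trial with two arms".

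**The concern.** Once patients have switched, the group randomized to hyoscyamine is no longer the group treated with hyoscyamine. Section 5.3 cites ITT as the reason that crossover does no harm. That holds for a comparison of initial assignments. It does not hold for the drug-level statement in section 5.4.

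The direction matters because this is a non-inferiority trial. If hyoscyamine is the weaker drug, moving its unrelieved patients to tamsulosin makes the two arms look alike, and similarity is what the trial sets out to show. A trial run exactly to plan could report that hyoscyamine itself is non-inferior when the data show only that starting on it, with tamsulosin available as a fallback, is non-inferior.

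**Working it through.** **1. The plan's own figure.** Inputs from section 5.4: 47 per arm, CV .25, margin 15% of the mean USI, one-sided alpha .025, power 80%. A true difference of zero is my assumption, since none is stated. Working in units of the tamsulosin mean:

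- SE = .25 × √(2/47) = .0516
- margin/SE = .15/.0516 = 2.909, with 92 df
- power (noncentral t) = 82.1%

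The smallest n per arm reaching 80% is 45 on this scale. On the log scale with a margin of ln 1.15 it is 49 (normal) or 50 (t). No variant tried gives exactly 47, but 47 lies between these, so the sample size is not in question here.

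**2. Dilution on that scale.** Let the true drug deficit equal the margin, let c be the net share crossing from hyoscyamine to tamsulosin before the endpoint, and let e be the share of the tamsulosin effect that they gain. The arm difference shrinks from .15 to .15 × (1 − c·e). The ITT test then has noncentrality 2.909 × c·e.

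| Net crossover c | False non-inferiority, e = 1 | e = 0.5 |
|---|---|---|
| 0% | 2.5% | 2.5% |
| 10% | 4.7% | 3.5% |
| 20% | 8.3% | 4.7% |
| 30% | 13.6% | 6.3% |

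These are errors for the drug-level claim. For the comparison of initial assignments the rate is controlled at 2.5%.

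Crossover is open to both arms. If switchers in both arms gain the same amount, only the difference in rates counts, and equal rates give 2.5%. If tamsulosin switchers instead fall to the hyoscyamine mean, the dilution adds: 20% v 5% gives 10.7%.

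**3. On the planned primary endpoint.** Section 5.5 tests the change from POD1 to POD7 with a margin of 15% of that change. This is smaller than 15% of the mean whenever the mean change is smaller than the mean. The documents give neither the mean change nor its SD. I assume an SD of change of .25 of the mean, which keeps SE = .0516, and a deficit equal to the margin with e = 1. Noncentrality is margin × c/SE.

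| Assumed mean change (share of mean USI) | Margin | Noncentrality at c = 20% | False non-inferiority at c = 20% |
|---|---|---|---|
| 50% | .075 | .291 | 4.7% |
| 30% | .045 | .175 | 3.7% |
| 20% | .030 | .116 | 3.3% |

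**4. Who is affected.** Patients who switch between POD1 and the POD7 (or earlier removal) questionnaire have their endpoint score taken after the switch. Section 4.2 allows stents to stay in for up to 2 weeks, and the footnote in section 5.6 keeps the questionnaire on day 7 when removal is later. A patient who switches after POD7 therefore has both primary scores on the assigned drug.

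**5. At no true difference** the deficit is zero, there is nothing to dilute, and crossover adds no bias of this kind.

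**The case against.** The best defence is that the plan has already chosen a treatment-policy comparison. It uses the label comparative effectiveness, permits crossover expressly because the design is ITT, and analyses by randomized arm regardless of switching. On that view only loose wording remains. Much of this stands: ITT is valid for that question and should remain primary. But nothing in the plan limits the conclusion to starting treatment, and the wording that remains is the aim, the objective, the null and the planned conclusion.

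Two further points have weight. Crossover comes after rescue and may be rare or balanced before POD7; the documents do not say. And the diary records use of the study medications, while section 5.5 already tabulates additional medications, so crossover may be partly visible. One more table would show it, but no report of crossover by arm and day is planned.

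A reader might infer three stronger things, none of which the documents support:

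- **That ITT is the wrong analysis, or that the trial's error rate is 8% or 14%.** Those figures belong to the sample-size margin and to assumed crossover rates.
- **That no switcher has a score on the assigned drug after POD1.** This is untrue of anyone who switches after POD7.
- **That a per-protocol analysis would restore the .025 level, or should have to agree with ITT.** Switchers are selected on unrelieved symptoms. In simulation (deficit equal to the margin, 20% crossing from hyoscyamine only, full gain), a correlation of .5 between symptoms and crossing gave 12.3% false non-inferiority per-protocol against 8.5% for ITT. At .7 the figures were 20.8% and 8.6%.

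**Conclusion.** The mismatch stands: the planned test answers a question about initial assignment with switching allowed, while the aim, null and conclusion speak of the drug. The comparative-effectiveness label softens this but does not remove it.

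The possible error runs in one direction only under stated conditions: hyoscyamine truly worse, and net movement to tamsulosin before the endpoint questionnaire. Its size is not established. The illustrations reach 13.6% on the sample-size scale at 30% net crossover, and 3.3% to 4.7% on the change scale at 20%. All of them rest on assumed crossover. The change-scale figures rest also on an assumed mean change and SD.

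This should be corrected, with medium confidence about its practical importance. It is not a fault in the primary test.

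**What to change.** Leave the crossover rule, the primary ITT test and the sample size as they are.

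1. In section 5.5, state that the ITT result supports a conclusion about initial assignment to hyoscyamine or tamsulosin with switching allowed. Bring the wording of sections 1.1, 3.1 and 5.4 into line.
2. From the daily diary, report crossover by arm and day, separating switches before the POD7 (or earlier removal) questionnaire from later ones.
3. Pre-specify one supportive analysis: the same non-inferiority comparison in patients who did not take the other study drug before that questionnaire. Report it as an estimate with confidence interval beside the ITT result, and do not make the claim depend on it. State that switchers are selected on unrelieved symptoms, so it can be biased in either direction, and that it does not remove the effect of narcotic or Pyridium rescue.

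A sensitivity analysis that imputes post-switch scores with an added worsening is optional.

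**Cost.** A little more analysis of data already collected, and a narrower claim. The supportive estimate is less precise. With 20% crossing from one arm (47 v 38), SE = .25 × √(1/47 + 1/38) = .0545, about 6% larger than .0516. With 20% crossing in both arms (38 v 38), it is .0574, about 11% larger.

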# 4.2 EXCLUSION CRITERIA

- 1. Patients younger than 18 years of age
- 2. Patients with chronic or pre-existing indwelling stents
- 3. Patients currently receiving anticholinergic or alpha blocker therapy
- 4. Patients with chronic opioid or analgesic usage
- 5. Patients with chronic pain syndrome or symptomatic benign prostatic hyperplasia
- 6. Patients with an active untreated urinary tract infection
- 7. Patients who are currently pregnant or nursing
- 8. Patients with allergies or contraindication to either tamsulosin or hyoscyamine
- 9. Patients on active chemotherapy
- 10. Patients currently receiving other investigational therapy
- 11. Patients who are unable to sign consent/answer questionnaire due to compromised mental capacity or language barrier (the questionnaire is not validated in other languages)
- 12. Patients who have a stent placed emergently for an obstructing stone or septic stone without immediate stone removal,

13. Any stents placed that will stay in for longer than 2 weeks, including patients who suffered a ureteral injury (Grade 2 or above) during the procedure that will be classified as a screen fail

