The first arm is hyoscyamine 0.125 mg tab sublingual every 4 hours as needed for discomfort, and the second arm is tamsulosin 0.4mg tab orally daily. Both dosing regimens are standard prescription orders. Both medications are routinely used in our practice, so patients are not being exposed to new safety risks compared to non-study patients. Risks are reasonable, as the medications used in this study are already commonly used in our daily practice. Patients will be given contact numbers for the Urology Department should they have any adverse side effects or concerns. Hyoscyamine is an anticholinergic and can cause side effects including constipation, dry mouth, drowsiness, headache, or lightheadedness. Tamsulosin is an alpha blocker and can

cause side effects including dizziness, fatigue, nasal congestion, syncope and retrograde ejaculation. Patients who have taken alpha blockers are at risk for intraoperative floppy iris syndrome if they are going a cataracts surgery in the near future. Patients will be advised to immediately stop the medicine and seek medical care if they develop the rare but severe reactions of skin rash, swelling, confusion, irregular or fast heartbeat, eye pain, or hallucinations. As part of the standard treatment pathway for post-stent insertion, patients are also sent home with a narcotic pain medication to help with pain and discomfort. Our pathway is to prescribe all patients with 10 tabs of Norco 5/325 1-2 tabs po q6H PRN unless there are contraindications or allergies to this specific narcotic, in which case they are prescribed an alternative narcotic with Percocet 5/325 1-2 tabs po q6H PRN. Patients will be given a drug diary to document their usage of the study medications for stent discomfort, including their narcotic usage, so that this information can be tracked as well. Patients will stop drug diary at time of stent removal.

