Questionnaires will be completed either in person if patient is in clinic or inpatient, or via a REDCap survey prior to stent placement, POD1, POD7 or at the time of stent removal if the removal occurs prior to day 7, and POD30. Patients with strings attach to stents will be included as there is no literature to suggest that strings cause additional stent irritation. Both medications will be stopped once the ureteral stent is removed as part of routine urological follow-up care for the primary etiology. Once the number of study participants reaches the pre-determined goal as calculated by our biostatistician, study enrollment will conclude and we will begin analyzing the data.

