# **5.6 SCHEDULE OF EVENTS**

Visits	Enrollment	Stent Placement	POD1	POD2	POD3	POD4	POD5	POD6	POD7 A	POD30
USSQ	Х		Х						Х	Х
Randomization	Х									
Complete Medication Diary		Х	Х	Х	Х	Х	Х	Х	Х	
REDCap Survey			Х						Х	Х
Stop Medication									Х	

Footnotes: A = If stent is removed prior to day seven then USSQ will occur on day of stent removal and diary will be stopped. If stent is removed after day seven then USSQ will occur on day seven but the diary will be stopped on day of stent removal.

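### For stents removed after day 7, the text and the schedule of events give different points for stopping study medication, and footnote A does not settle it

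*Combined protocol and SAP*

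**What the plan says.** Five places in the combined protocol and SAP bear on when study drug and diary end.

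- **Section 5.3, text on medication:** "Both medications will be stopped once the ureteral stent is removed". The rule covers both drugs and carries no day limit.
- **Section 5.6, schedule:** the "Stop Medication" row has a single mark, in the POD7 column.
- **Section 5.6, footnote A, attached to the POD7 column:** for early removal, "If stent is removed prior to day seven then USSQ will occur on day of stent removal and diary will be stopped"; for late removal, "If stent is removed after day seven then USSQ will occur on day seven but the diary will be stopped on day of stent removal". Neither sentence mentions study medication.
- **Section 4.2, item 13:** excludes "Any stents placed that will stay in for longer than 2 weeks". Stents removed between day 8 and day 14 are therefore eligible.
- **Section 5.3, text on the diary:** "Patients will stop drug diary at time of stent removal". This agrees with footnote A.

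Section 5.5 then uses the diaries for the secondary endpoint: "The proportion of days that additional medications were used will be calculated for each group and 95% confidence intervals will be calculated". It sets no cut-off at POD7 and does not define the denominator.

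**The concern.** A patient whose stent is still in place after day 7 continues study drug under the section 5.3 text and stops it at POD7 under the schedule row. Site staff working from the table and staff working from the text could treat such patients differently without either departing from the document in front of them.

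The diary runs to removal under both instructions. Days after POD7 would therefore enter the additional-medication endpoint on study drug for some patients and off it for others. If the need for narcotics or Pyridium differs between those two states, the endpoint would mix them, and the analysis section does not say how to tell them apart.

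**Working it through.** The plan states no figure on this point, so there is nothing to reproduce. The check compares the instructions and then counts the diary days.

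**Step 1. The instructions by time of removal.**

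| Item | Removal before day 7 | Removal on days 8 to 14 |
|---|---|---|
| Study drug, section 5.3 text | stops at removal | stops at removal |
| Study drug, schedule row | mark at POD7 | mark at POD7 |
| Study drug, footnote A | silent | silent |
| Diary, section 5.3 and footnote A | stops at removal | stops at removal |
| USSQ, footnote A | day of removal | day 7 |

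Footnote A separates POD7 from removal in both directions, but only for the questionnaire and the diary. Read literally, it leaves the medication mark at POD7.

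**Step 2. Which analyses the conflict reaches.** The primary analysis in section 5.5 uses the "change in USI between POD1 and POD7 (or day of stent removal if removed before day 7"). For late removals, both instructions keep the patient on study drug up to POD7, so days after POD7 do not enter. The tests on the other USSQ domains also run from POD1 to POD7. At POD30, drug has stopped under either instruction. For removal before day 7, the USSQ window and the diary both close at removal, so the silence of footnote A there is a gap in conduct and not in the analysis. What remains is the diary-based secondary endpoint for late removals.

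**Step 3. Diary days affected per patient.** The schedule marks the diary from the day of stent placement. Let removal be on POD D, with D from 8 to 14, and count both the placement day and the removal day.

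- Total diary days = D + 1
- Days after POD7 = D − 7
- Share = (D − 7)/(D + 1)

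| D | Days after POD7 | Total diary days | Share |
|---|---|---|---|
| 8 | 1 | 9 | 11% |
| 11 | 4 | 12 | 33% |
| 14 | 7 | 15 | 47% |

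If the placement day is left out, the maximum is 7/14 = 50%. Section 5.5 does not say which count applies.

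**Step 4. The trial as a whole.** The documents do not give the share of patients with removal after day 7. The share of pooled diary days in question is an average of the per-patient shares weighted by diary length. It therefore lies between 0 (every stent out by day 7) and 7/15 (every stent out on POD14), and the documents do not narrow it further. They also give no rate of additional medication on or off study drug, so the shift in the endpoint cannot be calculated.

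**The case against.** The best case for the plan is that its parts point to one reading. Section 5.3 has an explicit sentence, whereas the schedule has only a mark. The table has no column for stent removal, so POD7 is a natural place to put a removal-day event. The footnote is attached to the column header, which suggests that the column moves with removal. The last diary mark also sits at POD7, although the diary plainly runs on. Finally, section 5.3 has the diary record use of the study medications, so extending the diary to removal fits with drug continuing until then.

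This is plausible, and it softens the conflict. It does not remove it, because no sentence says that POD7 stands for the removal day, and the one footnote written for late removals moves the diary and leaves medication out.

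The objection stands in full on consequences. A reader might infer a bias between the arms. The documents do not support that: both instructions apply alike to both arms, and nothing shows that one arm would be handled differently. Hyoscyamine is also taken as needed, so that arm can have drug-free days before POD7 in any case, and the contrast between days on and off drug is not clean there. The endpoint is secondary and examined mainly by descriptive statistics. Mixed days arise only if some staff follow the schedule mark and others the text.

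**Conclusion.** The inconsistency is real and confined to patients with stents removed on days 8 to 14. For each of them, 1 to 7 diary days, at most 7 of 15 (about 47%), have an undetermined treatment status in the additional-medication endpoint. This assumes that removal on POD14 counts as within 2 weeks, and that the placement and removal days are both diary days.

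Two stronger conclusions may be tempting. One is that the non-inferiority result is at risk; it is not, since its window closes at POD7 or earlier. The other is that diary days after POD7 must be dropped from the comparison. That does not follow. If the reconciled rule ties stopping to removal, treatment and diary periods coincide and a restriction would change nothing. If it does not, excluding those days is an analysis preference and not the correction of an error.

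This is a conflict about treatment conduct that should be corrected, with a limited and unsized effect on one secondary, descriptive analysis. Which stopping rule is right is not a question for this review.

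**What to change.** 1. Reconcile the section 5.3 text, the schedule row in section 5.6 and footnote A, so that a single stopping rule, chosen by the investigators, applies to both arms.
2. Extend footnote A to state that rule for medication, both for removal before day 7 and for removal after it.
3. Only if the reconciled rule leaves diary days after study drug has stopped, add a sentence to section 5.5 on how those days are counted, for example by tabulating them separately by randomised arm. This keeps every patient in the arm assigned.

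The cost is a correction to the text or table, an addition to the footnote and at most one sentence in section 5.5. No extra data are needed: stent duration and diary information are already collected under section 5.3.
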